3. SUBJECTS OF STUDY

There is an increase in the prevalence of cervicalgia related to postural habits, new work practices and the use of electronic devices, traffic accidents and population aging. Cervical pain is very frequent with a point prevalence between 10-13%, appearing at some point in life up to 70% of the population. Occurs between 11-14% of sick leave. This situation justifies the feasibility of obtaining the sample required to carry out the study in an adequate time. The sample required for this project according to similar articles will be around 30 subjects per group.

The selection criteria of the sample in this study are as follows.

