5.2. Dependent variables

The dependent variables of the study are Romberg index and stabilometric data with open eyes and closed eyes of the variables as follows:

- Mean of the oscillation on the X axis and on the Y axis.
- Length of the oscillation.
- Surface of the ellipse.
- Speed of the oscillation on the X axis and on the Y axis.
- Average speed of the oscillation.

6. STUDY GROUPS.

The sample will be divided into 2 groups: Intervention Group and Control Group. The suboccipital inhibition technic described will be applied to the intervention group. The control group will be given a superficial contact in the same area as the intervention, to rule out the exteroceptive effect associated with the therapist's contact. The subjects will be assigned to both groups through a computerized system of simple randomization.

7. EVALUATION.

The evaluation will be done at the Clinica Osteomed physiotherapy center located in Elche, where tools, space, evaluators and appropriately prepared interveners are available to carry out this project. The evaluation will be carried out in two moments: before the intervention and immediately after it. The time between the pre-intervention measurement and the intervention is less than 15 minutes. The time elapsed between the intervention and the post-intervention measurement will be less than 1 minute. For the evaluation a pressure platform will be used (Diagnostic Support SRL, model "Clinical MultiSensor", 4 sensors / cm², 40 captures / second) and the data will be registered by the Milletrix software (Diagnostic Support V.1.0.0.26). The stabilometric record will be made with aligned heels in a comfortable position for the subject, looking forward at eye level on a wall 5 m from the subject. On both sides there will be two clear panels that will close a 3 m wide corridor. It will remain silent, constant temperature (20°-23°) and good luminosity (2000 Lux). The stabilometric record will have a duration of 52 seconds. The measurement will be made without footwear and the orders given to the subject will be protocolized so that they do not influence their postural attitude unequally.

Stabilometric data with open eyes and closed eyes of the variables, mean of the oscillation on the X axis and on the Y axis, length of the ball, surface of the ellipse, speed of the oscillation on the X axis and on the Y axis, average speed of the oscillation and the Romberg index.

8. STUDY SEQUENCE.

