9. PROVIDED BENEFITS

The technique proposed in this study should have an impact on the symptoms of instability and balance disorders associated with cervicalgia. The technique under study may be included in the protocols of conservative physiotherapy treatment for patients with cervicalgia and cervicogenic instability.

Statistical Analysis Plan (SAP)

Size Sample and Feasibility

The statistical program that we will use will be SPSS v.20. To determine the sample size, a pilot study will be conducted with the same methodology as the original study to a group of 10 subjects. These subjects will be assigned to the same group. This pilot study will provide us with the estimates of the mean and variance of the response variable, thus being able to calculate the appropriate sample size by determining a minimum power value of 80% ($W > 80\%$) and a confidence level of 95% ($p < 0.05$).

The pilot sample will be part of the final sample to be studied if there are no changes in the protocol or in the variables to be measured.

For the descriptive analysis, the mean and the standard deviation will be calculated. To prove normality, the Kolmogorov-Smirnov test, or Shapiro-Wilk test, and for homoscedasticity the Levene test. To evaluate the pre-post intra-group differences, the t test will be used for related samples (if they are parametric) or the Mann-Whitney U test (if they are nonparametric). For the analysis of pre-post intergroup differences the ANOVA statistic will be used. The significance value is set at $p < 0.05$.

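### Levene's test triggers no action and the between-group test is fixed as equal-variance ANOVA although the arms are likely to be unequal; Welch's test would remove the modest error-rate risk at almost no cost

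*Combined protocol and SAP*

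**What the plan says.** The analysis paragraph of the SAP lists an assumption check, "for homoscedasticity the Levene test", and does not say what follows if it rejects. The only parametric/nonparametric branch in that paragraph belongs to the within-group comparison. For the comparison between arms the method is fixed: "For the analysis of pre-post intergroup differences the ANOVA statistic will be used". No unequal-variance version is mentioned.

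Three other statements bear on arm sizes:
- Section 6 (Study groups): "The subjects will be assigned to both groups through a computerized system of simple randomization". No blocking or other restriction is described.
- Section 3 (Subjects of study): "The sample required for this project according to similar articles will be around 30 subjects per group".
- SAP, sample size paragraph: a pilot of 10 subjects, all placed in one group, sets the final size. These subjects are kept in the final sample if the protocol and variables do not change.

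No SD is given for any outcome. The SAP leaves this to the pilot: "This pilot study will provide us with the estimates of the mean and variance of the response variable".

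**The concern.** A check without a consequence leaves the analyst two options if Levene's test rejects: ignore it, or choose a remedy after seeing the data. The plan should settle this beforehand, because the between-group comparison is the one that answers the trial's question.

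The choice can matter numerically. Pooled ANOVA estimates one common variance. If the arms differ in size, that estimate is dominated by the larger arm. The standard error of the difference is then too small when the smaller arm is the more variable one, and too large in the opposite case. At stake are the real error rate of the 5% rule at the split obtained and, when there is an effect, the width of the confidence interval.

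**Working it through.** **Inputs.** From the documents: about 30 per group (Section 3), simple randomisation to two groups (Section 6), 5% significance, 80% power and 10 one-group pilot subjects (SAP). Assumed, because not stated: total 60, 1:1 ratio, two-sided test, normal data, no dropout, and an SD ratio between arms of 1.5 to 2. With two groups and two time points, the group-by-time F test is the square of the pooled t test on change scores, so the calculation uses that test.

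**The plan's own figure.** The 30 per group cannot be reproduced, since no effect size or SD is given. Solving backwards, d = (1.960 + 0.842) × √(2/30) = 0.72, the standardised difference that 30 per group detects with 80% power.

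**Arm sizes, Binomial(60, 0.5).**
- Smaller arm 27 or fewer: 51.9%
- Smaller arm 25 or fewer: 24.5%
- Smaller arm 24 or fewer: 15.5%, so both arms lie within 25 to 35 in 100 − 15.5 = 84.5%
- Smaller arm 22 or fewer: 5.2%
- With the 10 pilot subjects kept in one arm and 50 randomised: expected split 10 + 25 = 35 against 25

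**Why the split matters: one case by hand.** Take 25:35, with SD 2 in the smaller arm and 1 in the larger.
- Pooled variance: (24 × 4 + 34 × 1)/58 = 2.241
- Variance of the difference assumed by ANOVA: 2.241 × (1/25 + 1/35) = 0.154
- True variance: 4/25 + 1/35 = 0.189
- The standard error is √(0.154/0.189) = 0.90 of what it should be.

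With the SDs swapped:
- Pooled variance: (24 × 1 + 34 × 4)/58 = 2.759
- Assumed variance 0.189, true variance 1/25 + 4/35 = 0.154
- The standard error is 1.11 times what it should be.

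At 30:30 the assumed and true variances coincide: 2.5 × 2/30 = 4/30 + 1/30.

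**Simulated Type I error at nominal 5%** (400,000 replicates per setting; equal means, unequal SDs; runs agree within about 0.1 point):

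| Split | SD ratio | ANOVA, smaller arm more variable | ANOVA, larger arm more variable |
|---|---|---|---|
| 30:30 | 1.5 | 5.0% | 5.0% |
| 30:30 | 2 | 5.2% | 5.1% |
| 27:33 | 1.5 | 6.0% | 4.3% |
| 27:33 | 2 | 6.6% | 3.9% |
| 25:35 | 1.5 | 6.6% | 3.8% |
| 25:35 | 2 | 7.8% | 3.2% |
| 22:38 | 2 | 9.6% | 2.3% |

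Welch's test stays at 4.9% to 5.1% in all of these settings.

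**Averaged over the possible splits.** Simple randomisation of all 60: 5.2% at SD ratio 1.5 and 5.3% at ratio 2. Pilot kept in one arm and 50 randomised: 6.8% or 3.8% at ratio 1.5, and 8.0% or 3.3% at ratio 2, depending on which arm is more variable.

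**Levene's test as a safeguard.** At 25:35 and SD ratio 1.5 it rejects in only about half of samples.

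**Power under imbalance, equal variances.** At 25:35: 0.723/√(1/25 + 1/35) − 1.960 = 0.80, which is 78.9% against 80% at 30:30. At 22:38 it is 77.0%.

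**The case against.** The strongest reply concerns where unequal variance would come from. If the technique does nothing to anyone, randomised arms have equal variances and ANOVA holds 5% at any split. If it works in only some subjects, the spread grows but the mean normally moves too, and rejecting is then no false positive. Suppose half the subjects respond by a constant amount. The variance ratio is 1 + 0.25 × response². An SD ratio of 1.5 then needs a response of √(1.25/0.25) = 2.2 SD and a mean shift of 1.1 SD. This stands. The tabulated error rates describe equal means with unequal spread, as when gains and losses cancel. Outside that case the issue is a wrong standard error and interval width.

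Three stronger readings might be inferred, and the documents do not support them.
- That the planned 30 per group is rarely reached. Exactly 30:30 has a probability of only 10.3%, but the plan says "will be around 30 subjects per group". Both arms fall within 25 to 35 in 84.5% of trials, and 25:35 costs about 1 point of power.
- That the ANOVA is in general far from 5%. Under simple randomisation alone it averages near 5%. A large distortion needs both a marked imbalance and a marked SD difference.
- That blocked randomisation is required. Simple randomisation is valid. Section 8 has the treating intervener also perform the randomisation, so blocks would make later allocations easier to guess, and Welch's test controls the error rate without them.

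The reply does not remove the gap in the text: the check has no consequence and the between-group test has no alternative.

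**Conclusion.** The point holds as an inexpensive improvement to the SAP. Levene's test leads nowhere, and the equal-variance ANOVA is fixed for arms that are likely to be unequal: by chance under simple randomisation, and systematically (about 35:25) if the pilot subjects are retained. For SD ratios of 1.5 to 2, the real error at the split obtained runs from 3.9% to 6.6% at 27:33 and from 3.2% to 7.8% at 25:35. With the pilot retained, the averages run from 3.3% to 8.0% and no longer settle near 5%.

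This rests on a total of 60, 1:1 allocation, normal data, no dropout and assumed SD ratios. The retained-pilot figures also require that all 10 stay in one arm; the SAP does not say which arm, so the direction is unknown. The expected effect is modest, and the trial's validity does not turn on it.

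**What to change.** State in the SAP that the between-group comparison of pre-post change uses Welch's unequal-variance test for every variable, or heteroscedasticity-robust standard errors if a covariate is added. Remove Levene's test as a decision step. It may stay as description, but nothing should depend on it.

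The cost is one sentence of wording. With equal variances, the power loss against the pooled test is under 0.1 point at 30:30 and about 0.5 point at 22:38. The allocation method need not change for this purpose.

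Welch's test deals only with the effect of unequal arm sizes on the standard error. It does not answer the separate question of including non-randomised pilot subjects in a randomised comparison.

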1. OBJECTIVES

The objectives of our study are the following:

General:

- Check whether the technique of suboccipital inhibition influences suboccipital rachis proprioceptivity enough to modify postural balance.

Specific:

- Evaluate immediate changes in the oscillation of the center of gravity when standing after the suboccipital inhibition technique.
- Check the variation of the Romberg coefficient after the suboccipital inhibition technique.

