The study will be carried out in two adjoining rooms with enough space to offer freedom of movement to both the examiner and the subject of study. In one of them will be the evaluator, responsible for making the measurements and collect the pre-intervention and post-intervention values, using a stabilometric platform, a scale with stadiometer and a computer. The time that elapses between the execution of the technique and the start of the post-intervention measurement is, in all cases, less than one minute. In the other room, the intervener will be in charge of performing the randomization after the first measurement and performing the corresponding intervention. It will have a treatment table for the patient and a stool for the intervener. Between both rooms there are approximately eight meters without steps or unevenness.

A. Recruitment: Recruitment will be done after the first physiotherapy consultation. The

physiotherapist will inform the patient of the characteristics of the study and, after checking their eligibility to participate in the study, will proceed to sign the informed consent.

B. Evaluation pre-intervention. The subject of the study begins his participation in the evaluation room. The evaluator performs the pre-intervention evaluation. Following the protocol of the "Association Française de Posturologie" (AFP) the subject will be in a well-lit room (2000 Lux approximately), located on the platform with the heels separated 4 cm and with the tips of the feet forming a 30° angle. You will look forward to a fixed point located 5 meters above your eyes. On both sides, two light colored panels are placed. The width of the tunnel thus formed is 3 meters. In addition the room will be silent and the temperature will be constant between 20° and 23°C so that the physiology of the subject is not altered to the point of feeling cold or sweating. We have decided to use this protocol because they are healthy subjects because, despite being an artificial position, we unify all the subjects in a position of certain instability because their heels are very close and their feet are symmetrical. Each foot is separated 15° of the sagittal plane. We will make the assessment with open eyes and closed eyes to determine the Romberg coefficient.

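### Both specific objectives are before-after changes with no comparator, and the SAP tests within and between groups at p<0.05 without saying that the between-group result decides.

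*Combined protocol and SAP*

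**What the plan says.** Section 1 (Objectives) gives two specific objectives: "Evaluate immediate changes in the oscillation of the center of gravity when standing after the suboccipital inhibition technique" and "Check the variation of the Romberg coefficient after the suboccipital inhibition technique". Neither mentions the control group. The general objective is causal, asking whether the technique acts on proprioception strongly enough to alter balance, but it names no comparator either.

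The analysis paragraph of the SAP (under Size Sample and Feasibility) plans two inferential steps. Within groups: "To evaluate the pre-post intra-group differences, the t test will be used for related samples", with a non-parametric alternative. Between groups: "For the analysis of pre-post intergroup differences the ANOVA statistic will be used". One significance level, p<0.05, covers both. The SAP names no primary analysis and no decisive test, and it does not restrict the within-group tests to description. Its sample-size sentence sets an 80% power target without attaching it to either test.

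Section 6 gives the control group a superficial contact in the same area. Section 4 has the technique done supine, with pressure held for 4 minutes. Section 8 puts measurement and intervention in separate rooms: "Between both rooms there are approximately eight meters without steps or unevenness". The second record starts less than one minute after the technique.

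**The concern.** Of the two planned tests, the one that matches the wording of the specific objectives is the uncontrolled one. A before-after difference in the technique arm contains any effect of the technique plus everything else that separates the two records: a second exposure to the platform, a period lying down, getting up, and the walk between rooms. A one-arm test cannot separate these.

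Two misreadings are left open. The first declares an objective met because the technique arm changed significantly. The second infers an effect because the technique arm changed significantly and the control arm did not. That pattern is not a test of the difference between the arms. Either could be reported alongside a null ANOVA without departing from the plan. Section 9 anticipates that the technique may enter conservative treatment protocols, so the conclusion should rest on the randomized comparison.

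**Working it through.** **Inputs from the documents**
- Group size: "The sample required for this project according to similar articles will be around 30 subjects per group" (section 3).
- Significance level: 0.05 (SAP). Sidedness is not stated; two-sided is assumed.
- Power target: 80% (SAP).

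**Assumptions, because the documents give no figures**
- Exactly 30 per arm. Simple randomization does not guarantee this.
- Normally distributed change scores.
- No technique effect.
- The same non-specific shift in both arms, written d and measured in SDs of the change score. The main range is 0.2 to 0.4.

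**The plan's own figure.** Thirty per group cannot be reproduced, since no effect size or SD is given. It can be turned round. With n = 2(1.960 + 0.842)²/d² = 15.70/d² per group, a between-group standardized difference of 0.73 needs 15.70/0.533 = 29.5, so 30. The t-based solution is 0.736. Thirty per group therefore gives about 80% power for a between-group difference of about 0.73 SD.

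**Paired test in the technique arm.** The statistic follows a noncentral t distribution with 29 df and noncentrality d × √30 = 5.477d. The rejection probability p is the chance that its absolute value exceeds the two-sided 5% critical value (2.045). For d = 0.2, 0.3 and 0.4 the noncentrality is 1.10, 1.64 and 2.19.

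**Technique arm significant, control arm not.** The arms are independent and share the same p, so the probability is p(1 − p). For example, at d = 0.2 it is 0.185 × 0.815 = 0.151.

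**Between-group test on change scores.** The shared shift cancels, so the expected difference is zero at every d and the rejection rate is nominally 5%. A simulation of 100,000 trials per shift gave 4.9% to 5.1% at shifts of 0, 0.2, 0.3, 0.5 and 0.8.

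| Shared shift (SD of change) | Paired test significant, technique arm | Technique arm significant, control not | Between-group test |
|---|---|---|---|
| 0 | 5.0% | 4.75% | about 5% |
| 0.2 | 18.5% | 15.1% | about 5% |
| 0.3 | 35.5% | 22.9% | about 5% |
| 0.4 | 56.3% | 24.6% | about 5% |
| 0.5 | 75.4% | 18.6% | about 5% |

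The 0.5 row shows how sensitive the first column is to the assumed shift. The second column falls there because both arms then tend to be significant.

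These rates are per outcome. Section 5.2 lists seven stabilometric measures, each with eyes open and closed, plus the Romberg index: 7 × 2 + 1 = 15 outcomes.

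**The case against.** The strongest reply is that the plan already contains the right comparison. The SAP schedules a between-group ANOVA of pre-post differences. Section 2 calls the study a randomized controlled trial, section 5.1 lists group and time as the independent variables, and section 6 provides a sham contact. A group-by-time analysis is a plausible reading of all this, and nothing says that the within-group tests decide. Planning within-group tests next to a between-group test is not an error in itself; concluding from them is.

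Much of this stands. A reader might infer that no controlled comparison is planned, or that the plan makes the within-group result decisive. The documents support neither. The fault is narrower: nothing makes the ANOVA decisive, and the specific objectives point to the other test. Nor can the within-group tests be passed off as description, because the SAP has a separate descriptive step (mean and SD) and treats these as hypothesis tests.

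Three further limits apply.
- **Counting exactly one significant arm.** This gives 2p(1 − p), which is 30% to 49% over the main range and 9.5% with no shift. Half of those trials have only the control arm significant and could not be presented as support for the technique. The relevant figures are 15% to 25%, and 4.75% with no shift, which is no excess over 5%.
- **The sham's purpose.** A reader might suppose that it was introduced to remove the effects of posture, walking and retesting. Section 6 states a narrower aim, to exclude the effect of the therapist's touch on the skin.
- **The equal shift.** The control subjects' position and contact duration are not stated, and section 8 says that the sequence differs by group from randomization onward. If the non-specific shift differs between arms, the one-arm pattern figures change and the between-group rate need not stay at 5%. That a one-arm test cannot isolate the technique does not depend on this assumption.

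**Conclusion.** The concern holds as a gap in how conclusions are to be drawn. The specific objectives lack a comparator, and the SAP gives within-group and between-group tests equal standing, so an uncontrolled change could be reported as meeting the objectives even with a null ANOVA. The text shows that this can happen, not that it will.

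If conclusions were drawn from the technique arm's paired test, the false-positive rate per outcome would be 19% to 56% for a shared shift of 0.2 to 0.4 SD. For the pattern of technique arm significant and control not, it would be 15% to 25%. The between-group test on change scores would hold at about 5%. These sizes rest on the assumed shift, its equality across arms, 30 per arm and two-sided testing. With no shift at all, neither within-group reading exceeds 5% per outcome. The gap should be closed before the data are analysed; it does not invalidate the design.

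**What to change.** 1. Reword both specific objectives as comparisons of the pre-post change between the intervention and control groups.
2. State in the SAP that only the between-group contrast supports a conclusion about the technique, and specify its form: the group effect on the post value adjusted for the pre value, or the group-by-time term.
3. Make within-group changes descriptive (mean change with 95% confidence interval) and say that they are not a basis for conclusions. Omitting their p-values is a reporting preference; the statement in item 2 does the essential work.

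It would also help to state the control subjects' position and contact duration as carried out, so that a reader can judge whether the non-specific influences are matched between arms.

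The cost is a few sentences in the objectives and the SAP. No new data, subjects or measurements are needed.

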2. STUDY DESIGN

A randomized controlled clinical trial of an explanatory, single-blind, blind appraiser strategy will be conducted (no relationship between evaluator and auditor). The subject will not know his group of belonging and, to strengthen his blinding, will not know how many measurements will be made. Participation in the study is free. The evaluation will be carried out before and immediately after the intervention.

All participants will be informed of the purpose of the study through an information document prepared for this purpose and will be clarified any doubts that may arise. After answering as many questions as necessary, the subject must sign the informed consent document to be part of the study. The principles of the Declaration of Helsinki (2004) will be respected at all times. The data collected will be treated confidentially by applying the current legislation on the protection of personal data (Organic Law 15/1999 of December 13, Protection of Personal Data) and / or any other applicable.

This study has been admitted by the Research and Ethics Committee of Cardenal Herrera CEU University Number CEI18/201

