C. Randomization and intervention. The subjects are subjected at that moment to the randomization process. From that moment on, the sequence differs according to the group to which the individual has been assigned (control or intervention).

D. Evaluation post-intervention. A second stabilometric measurement is carried out immediately after the application of the technique, concluding the individual study.

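### The SAP assigns the Mann-Whitney U test, which is for independent samples, to paired within-group pre-post comparisons; with positive pre-post correlation it is conservative and can miss real changes

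*Combined protocol and SAP*

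**What the plan says.** The analysis paragraph of the SAP has three relevant sentences.

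- **Assumption checks:** "To prove normality, the Kolmogorov-Smirnov test, or Shapiro-Wilk test, and for homoscedasticity the Levene test". It does not say whether normality is tested on the pre and post values or on their differences.
- **Within-group comparison:** "To evaluate the pre-post intra-group differences", the plan continues, "the t test will be used for related samples (if they are parametric) or the Mann-Whitney U test (if they are nonparametric").
- **Between-group comparison:** "For the analysis of pre-post intergroup differences the ANOVA statistic will be used".

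Section 2 (Study design) fixes the data structure: "The evaluation will be carried out before and immediately after the intervention". Section 8 (Study sequence), step D, confirms a repeat measurement on the same person: "A second stabilometric measurement is carried out immediately after the application of the technique, concluding the individual study". No paired rank test is named anywhere in the protocol or SAP.

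**The concern.** Pre and post values from one group are two readings on the same people. The Mann-Whitney U test assumes two independent samples, so its standard error includes between-subject variation that a paired analysis removes. The sentence is also inconsistent with itself: the related-samples requirement in its first half is dropped in its second.

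The within-group results are likely to be reported, because the specific objectives in section 1 are worded as change after the technique, for example "Evaluate immediate changes in the oscillation of the center of gravity when standing after the suboccipital inhibition technique". Section 5.2 lists seven stabilometric variables, each with eyes open and eyes closed, plus the Romberg index: 7 × 2 + 1 = 15 variables, or 15 × 2 = 30 within-group comparisons over the two groups. A normality p-value would send each of these to a paired or an unpaired test, so sensitivity would differ between outcomes for no scientific reason. A non-significant change in the control group could also be misread as stability when the test was merely insensitive.

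**Working it through.** **Which comparison the test serves.** The Mann-Whitney clause belongs to the sentence on within-group differences. The next sentence gives the between-group comparison to ANOVA, so the clause cannot be read as a between-group test.

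**Inputs from the documents.** About 30 subjects per group (section 3); significance level 0.05 and minimum power 80% (SAP). The plan's sample size cannot be reproduced, because no effect size, standard deviation or correlation is given. The point does not depend on it.

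**Assumptions.** Two-sided testing; 30 pairs; equal pre and post variance; pre-post correlation ρ of 0.3, 0.5 or 0.7. A positive ρ is plausible: the same person stands on the same platform less than 15 minutes before the intervention and less than 1 minute after it (section 7).

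**Direction of the error.** The variance of the mean change is 2σ²(1 − ρ)/n. An unpaired test acts as if it were 2σ²/n. The test statistic therefore has standard deviation of about √(1 − ρ) instead of 1, and the actual two-sided error rate is about 2 × [1 − Φ(1.96/√(1 − ρ))]:

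- ρ = 0.3: 1.96/√0.7 = 2.34, giving 1.9%
- ρ = 0.5: 1.96/√0.5 = 2.77, giving 0.6%
- ρ = 0.7: 1.96/√0.3 = 3.58, giving 0.03%

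This is a large-sample approximation for normal data. Simulation of the Mann-Whitney test itself gives slightly higher values (next table). With negative correlation the direction reverses: at ρ = −0.3 the simulated error rate is 7.9%.

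**The two tests head to head.** Simulation with 20,000 replicates and normal data. The mean change is 0.529 standard deviations of the difference, which gives 80% paired-t power with 30 pairs.

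| ρ | Type I error, Mann-Whitney | Type I error, signed-rank | Power, Mann-Whitney | Power, signed-rank |
|---|---|---|---|---|
| 0 | 4.9% | 4.9% | 79.6% | 78.2% |
| 0.3 | 2.4% | 5.3% | 66.5% | 78.4% |
| 0.5 | 0.7% | 4.9% | 50.9% | 78.4% |
| 0.7 | 0.1% | 5.1% | 23.8% | 78.1% |

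Log-normal data (log-SD 0.5) give nearly the same result: power 66%, 50% and 24% for Mann-Whitney, against 76%, 76% and 75%. At 1.5 times the effect (normal data) the gap narrows: 96%, 91% and 72% against 98%.

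**How to read the power column.** The effect is fixed in units of the SD of the difference, so the shift in raw SD units is 0.529 × √(2(1 − ρ)): 0.75 at ρ = 0, 0.63 at 0.3, 0.53 at 0.5 and 0.41 at 0.7. Part of the fall in Mann-Whitney power is this smaller raw shift. If the raw shift is instead held at 0.5 SD, Mann-Whitney power stays at 43% to 45% for ρ from 0 to 0.9. Signed-rank power rises from 45% (ρ = 0) to 59% (0.3), 74% (0.5) and 91% (0.7). The gap is present under either scale.

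**The SAP's whole rule.** Shapiro-Wilk first, then the paired t or Mann-Whitney test, at the same 80%-power effect. Figures are for ρ = 0.3, 0.5 and 0.7.

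| Data and rule | Nonparametric branch entered | Power |
|---|---|---|
| Log-normal, check on raw pre and post values (either fails) | 92%, 91%, 89% | 67%, 53%, 29% |
| Log-normal, check on differences | 34%, 37%, 39% | 72%, 65%, 53% |
| Log-normal, check on differences, signed-rank instead | as the row above | 76%, 75%, 74% |
| Normal, check on raw values | about 10% | 79%, 77%, 76% |
| Normal, check on differences | about 5% | 79%, 79%, 77% |

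For normal data the comparators are 80%, 80% and 81%.

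**The case against.** The error does not touch the randomised comparison, which is what answers the general objective; within-group tests do not establish efficacy in a two-group trial. Given positive correlation, the error costs missed secondary changes and produces no false claims. For normal variables the SAP's rule seldom reaches the faulty branch, so the realised loss is only 1 to 5 percentage points. Large losses need substantial correlation and marked skew, and are worst when normality is checked on raw values. The documents give none of these quantities, and the 80% target in the SAP is not tied to within-group tests. The count of 30 comparisons is a ceiling, since the number that would be sent to Mann-Whitney is unknown. Finally, not saying what the normality check applies to is an ambiguity, not an error.

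All of this stands as a limit on the consequences. None of it makes the named test right for the data it is assigned to. An analyst who follows the SAP literally would run an unpaired test on paired data.

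**Conclusion.** The concern holds: the nonparametric branch of the within-group analysis names the wrong test and must be corrected before analysis. Under positive pre-post correlation the test is conservative, with an actual error rate of about 2%, 0.7% and 0.1% at correlations of 0.3, 0.5 and 0.7 against a nominal 5%. Within that branch, power is about 67%, 51% and 24% against 78% at the reference effect. Under the full two-step rule, the power lost on skewed variables runs from about 4 points (72% against 76%) to 45 points (29% against 74%), depending on the correlation and on what the normality check is applied to. At zero correlation nothing is lost.

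These sizes rest on 30 pairs and on assumed correlations, distributions and effects, so no single figure can be attributed to this trial. The choice of test being wrong does not depend on those assumptions. The between-group ANOVA is unaffected.

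**What to change.** In the within-group sentence of the SAP, replace the Mann-Whitney U test with the Wilcoxon signed-rank test. Add a clause stating that normality is assessed on each subject's post-minus-pre difference, since that is the quantity the paired t test relies on. The cost is one phrase and one clause; the design, the data collected and the between-group analysis stay as they are.
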